Subjects may also be active in IRB #6654R, 7132R, 7342 (PI [name] on them all) as they are longitudinal studies. However, no study procedures for the other studies will take place while active in the current study. Rather, the other studies are studies which involve an active period, followed by up to two years of longitudinal follow up before procedures are repeated (6654R is the screening/umbrella protocol for all COPE studies). Therefore, subjects will not actually be "active" in more than one study while part of the current study, and therefore subjects will finish this study before moving on to any other studies. Patients will be told about the study by staff at the COPE clinic (IRB #6654R). If interested, the study will be explained in greater detail by a study physician. **Healthy control subjects may also be recruited through 6654R or other Area Psychosis research studies though will only be active in one protocol at a time.**

Inclusion/Exclusion Criteria

Name the subject group/sub sample

Clinical High Risk

Create or insert table to describe the inclusion criteria and methods to ascertain them

Criterion	Method of Ascertainment
1. COPE Patient between the ages of 18-30 (Identified as at clinical high risk for psychosis as defined as a) attenuated psychotic symptoms; or b) brief intermittent psychotic symptoms c) schizotypal disorder or family history of psychotic disorder with recent decline in functioning (30 GAF points))	Structured Interview for Prodromal Syndromes/ Scale of Prodromal Symptoms (SIPS/SOPS)
2. Capacity to provide informed consent	Clinical assessment by research team and independent assessment of capacity
3. Currently using a reliable form of birth control (females and males)	Physician interview

Create or insert table to describe the exclusion criteria and methods to ascertain them

Criterion	Method of Ascertainment
1. Metal implants in body or a history of metal working	Physician evaluation
2. Lifetime diagnosis of asthmatic symptoms within the past 3 years or known sensitivity to contrast agents	Physician evaluation
3. Lifetime diagnosis of renal failure/disease	Physician eval and laboratories
4. Acute neurological, neuroendocrine, or medical disorder including renal insufficiency (CrCl <60mL/min/1.73m ²)	Physician exam, electrolytes, CBC
5. Lifetime diagnosis of hypertension or diabetes or seizure disorder	Physician evaluation
6. IQ < 70	WTAR < 6

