7. Acute risk for suicide and/or violence	Physician evaluation, suicidal or violent act in last 6 months, CSSRS
8. Pregnant, lactating	Urine pregnancy test
9. Current abuse of substances (alcohol, cocaine, stimulants, cannabis, opiates, sedative hypnotics)	SCID, utox
10. Current use or anticipated need for any antipsychotics or mood stabilizers (all antipsychotics, also Depakote, lithium, lamotrigine, pregabalin or any med with a mechanism of action like gabapentin) probenecid. Patients may take selective serotonin reuptake inhibitors, tricyclic antidepressants, and monoamine oxidase inhibitors as long as they have been on a stable dose for at least 4 weeks before starting study drug.	Physician Eval
11. More than one previous gadolinium scan	Physician Eval

Inclusion/Exclusion Criteria #2

Name the subject group/sub sample
 Controls

Create or insert table to describe the inclusion criteria and methods to ascertain them

Criterion	Method of Ascertainment
1. Healthy control between the ages of 18-30	Scid
2. Capacity to provide informed consent	Clinical assessment by research team
3. Currently using a reliable form of birth control (females)	physician interview

Create or insert table to describe the exclusion criteria and methods to ascertain them

Criterion	Method of Ascertainment
1. Metal implants in body or a history of metal working	metal screener
2. Any neurological disorder	medical history
3. IQ < 70	WTAR < 6 (only if IQ < 70 is suspected)
4. Pregnant, lactating	urine pregnancy test
5. Current use of substances (cocaine, stimulants, cannabis, opioids, sedative hypnotics)	utox, SCID
6. Any history of use of a psychiatric medication	History
7. Any history of a DSM Axis I disorder with the exception of specific phobias and adjustment disorders	SCID

Waiver of Consent/Authorization

Indicate if you are requesting any of the following consent waivers

Waiver of consent for use of records that include protected health information (a HIPAA waiver of Authorization)
No

Waiver or alteration of consent
No

Waiver of documentation of consent
Yes

Waiver of parental consent
No

Consent Procedures

Is eligibility screening for this study conducted under a different IRB protocol?

Yes

Indicate NYSPI IRB #

6654R

Describe Study Consent Procedures

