All COPE subjects receive up to 2 years of free, no cost treatment (medication management and therapy), though they would have to cover the cost of their medications.

Clinical Treatment Alternatives

Clinical treatment alternatives

If subjects clinically require active treatment for new onset mood syndrome (major depressive or bipolar, anxiety symptoms, or psychosis during the study period or screening phase) patients will be immediately offered such treatment. Subjects will be ineligible for study participation if they meet any exclusion criteria as a result of such clinical developments. Since POMA is an experimental medication, it will not be available to subjects at the end of the trial.

Patients in this study will continue their usual treatment with their usual psychiatrist and clinician without interruption or changes. There is currently no standard best clinical practice (psychotherapeutic or psychopharmacologic) for prodromal stages of psychotic disease. Available antipsychotic therapies have been studied and are associated with improved prodromal symptoms and lessening of transition to psychosis, but are associated with a significant side-effect burden, including EPS, weight gain, and hyperlipidemia, amongst other side effects. The evidence for efficacy of cognitive-behavioral interventions for prevention of transition to psychosis is also mixed to date.

Risks/Discomforts/Inconveniences

Risks that could be encountered during the study period

1) Risks and Discomforts Associated with LY2140023 (Pomaglumetd, "POMA") Administration

Approximately 582 healthy subjects and 2877 subjects/patients with schizophrenia have been exposed to POMA in prior studies. Across groups, nausea, vomiting, increased heart rate, and eosinophilia as assessed by laboratory values were commonly reported ($\geq 1\%$ and $< 10\%$) in patients treated with POMA.

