Healthy controls: 582 healthy control subjects received doses ranging from an acute dose of 5mg to 200 bid for up to 14 days. Most of the adverse events reported were mild, and the subjects recovered without sequelae. The most common AEs ($\geq 10\%$) in clinical pharmacology studies conducted in healthy subjects were: nausea, headache, vomiting, and dizziness. The following SAEs have been reported in healthy subjects: infected sebaceous cyst (1), deep vein thrombosis (1), pulmonary embolism (2), and syncope due to vasovagal event (1). With the exception of syncope due to vasovagal event, none of these SAEs were reported by the investigator as related to administration of POMA.

Most pertinent to the proposed dose in this study, multiple doses of POMA, administered up to 160 mg BID, were well tolerated in the healthy subject population, including 5 healthy controls receiving 160 mg BID (greater or equal 320 mg per day) for 14 days and 2 receiving 200

mg bid without significant side effects. There were no serious adverse events and all subjects completed. The most commonly reported adverse events were headache, nausea, epistaxis, diarrhea, dizziness, somnolence, tremor, pruritus and feeling hot. The profile of drug-related adverse events were similar to those reported in previous clinical pharmacology studies in healthy volunteers, and those reported in clinical studies with patient populations. There were no dose limiting events observed in doses up to 160 mg BID. The study was terminated prematurely by the Sponsor in response to two cases of convulsions observed in an ongoing Phase 2 study in schizophrenia patients, involving dose levels lower than doses administered in this study. Although no serious adverse events occurred the healthy control dose escalation study, the decision was taken to stop the study whilst the 200 mg dose level was ongoing

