Risk of Serotonin Syndrome

POMA increases levels of serotonergic metabolites in humans (Lowe et al., 2012) and therefore there is a theoretical increased risk of serotonin syndrome when POMA is administered with a serotonergic medication, such as an antidepressant. There is insufficient experience in humans to know whether this risk of more than theoretical. However, in order to protect against this risk, we will review serotonin syndrome as part of the standard consent process with all patients, include a full paragraph in risks section of the consent form discussing this theoretical risk, and review side effects at every visit, as previously described. In addition, we are already excluding individuals with any severe medical condition or history of seizure disorder, and have implemented a robust schedule for adverse event monitoring, including safety labs and medical/physical examination.

Seizure Risk

In all of the studies performed with POMA in human subjects, events of seizure were reported in 6 patients treated with POMA at 5, 20, and 80 mg BID. Additionally, seizures were reported in 1 patient randomized to risperidone and 1 patient during a placebo-lead in period. Seizures were reported in an additional 3 patients prior to them being randomized to study medication. There was 1 additional report of convulsion that was determined not to be seizures.

Specific Vulnerabilities

There are no known specific vulnerabilities for a CHR (**clinical high risk**) population. However, we will obtain an independent assessment of capacity for all subjects, and will also perform the SIPS and CGI and GAF weekly while in the study to follow clinical status.

Risks and Discomforts Associated with Compound LY404039 in Humans

A breakdown product of POMA, called LY404039, has been given to 24 healthy people in a previous study. Experiences reported by 2 or more people who have taken LY404039 were headache, feeling dizzy upon standing up, stomach pain, nausea (feeling sick to the stomach), sore throat, tiredness, or feeling sleepy.

Risks and Discomforts Associated with LY2140023 (Pomaglumetad, "POMA") in Animals

POMA has been studied in animals. Rats treated with POMA showed uncoordinated movement, problems with walking, reduced body weight, uncontrollable and rapid shaking (convulsions or

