possible seizures), or death. In 1 out of 40 rats treated with very high doses of POMA for 6 months, areas of brain injury were observed. Mice treated with POMA also showed uncontrollable and rapid shaking (convulsions or possible seizures). Vomiting, soft or watery stools, and/or a severe rash were seen in monkeys given high doses of POMA for up to 1 year. A single monkey was euthanized due to severe skin rash on Day 235 of the 1-year study. No convulsions have been observed in monkeys. In a study of the effects of POMA on pregnant rats and their offspring, some baby rats had significant decreases in their body weight, and some baby rats died up to 14 days after birth. The levels of drug in subject's blood will be lower than the levels of drug in monkeys at which the above bad effects were noted. Effects of convulsion observed in rats and mice were observed at blood drug levels that are similar to or lower than the levels expected in this study.

Summary

Doses of POMA as high or higher than the highest dose in this study (160 mg twice a day) have been taken by 24 healthy people without psychiatric illness for 10 days in a previous study without significant side effects. 44 patients with schizophrenia completed a multiple dose escalation study over a dose range of 160 to 480 mg BID for 7 days. Therefore, this dose and higher has been given before, but not for this length of time (14 days, though 7 and 10 days have been given).

2) Interviews and ratings (general): Study participants may feel anxious during medical history interviews or during administration of specific rating scales.

3) Brain imaging scans (general): It may be uncomfortable to lie motionless in the MRI scanner and it may cause some subjects to feel anxious.

4) Intravenous catheter: Intra-venous lines can cause pain, bleeding, or occlusion/clotting.

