The dosing guidelines for the brand of gadolinium to be used in this study are as follows: CNS (Central Nervous System) Adults: The recommended dose of Dotarem 0.1mmol/kg (0.2 mL/kg) administered as a rapid bolus intravenous injection. According to the Multihance package insert and the recent literature, repeated dosing of mutihance up to a total dose of .3mmol/kg (in three doses of 0.1mmol/kg) can be immediate given within a short time-span with no adverse effects. The elimination half-life of the compound is 1-2 hours. Prior to readministration, the FDA recommends 'sufficient time for drug elimination'. Our study design of a single baseline dose at 0.1mmol/kg followed by repeated injection 2 weeks later is more than adequate time for elimination of contrast agent, which should be complete by two days, and is well below the maximal dosing guidelines that have been shown to be safe with repeated dosing in prior studies.

COVID Risks There is a risk of exposure to COVID when deciding to go out in public and travel for research.

Describe procedures for minimizing risks

- 1) POMA: In order to minimize risk, we will exclude any individual with any history of seizure disorder, or any severe medical condition. We will obtain frequent laboratory analyses, including liver tests, and cbc, adverse event queries, and EKGs and temperature during this study. Patients will be terminated from the study if they develop side effects that are, in the opinion of the PI, preclusive of continuing in this protocol or in particular if they meet worsening criteria based on the CGI or need for prn medications.
- 2) Interviews and ratings (general) Participants will be allowed to take breaks as necessary and are not required to answer any questions that may be uncomfortable.
- 3) Brain imaging scans (general): Our staff will be available to provide support, reduce anxiety, optimize the comfort of the subject and remove the subject from the MRI magnet bore if requested.
- 4) Intravenous catheter: Placement risks are minimized by using proper techniques.

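### The written patient exclusions admit a person with one undiagnosed past seizure, or a chronic non-severe condition that predisposes to seizure, to a drug whose risk section lists seizures

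*Protocol*

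**What the plan says.** In the Protocol's Inclusion/Exclusion Criteria for the Clinical High Risk group, two of the 11 exclusions name a neurological condition. Exclusion 4 reads "Acute neurological, neuroendocrine, or medical disorder including renal insufficiency", with a creatinine-clearance limit attached to the renal part. Exclusion 5 reads "Lifetime diagnosis of hypertension or diabetes or seizure disorder". The section on procedures for minimizing risks says, for POMA: "In order to minimize risk, we will exclude any individual with any history of seizure disorder, or any severe medical condition". The serotonin-syndrome paragraph makes much the same statement.

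On the hazard, the Seizure Risk paragraph says that "events of seizure were reported in 6 patients treated with POMA at 5, 20, and 80 mg BID". It then lists seizures in 1 patient randomized to risperidone, 1 in a placebo lead-in period and 3 before randomization. The animal section describes "convulsion observed in rats and mice were observed at blood drug levels that are similar to or lower than the levels expected" in this study. Of an earlier healthy-volunteer dose study, the protocol says: "The study was terminated prematurely by the Sponsor in response to two cases of convulsions observed in an ongoing Phase 2 study".

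Criteria for Early Discontinuation lists seizure activity as a reason to stop. Study Procedures, item f, says that a gross structural abnormality on the scan is reported to the principal investigator and followed up clinically. It does not say what this means for eligibility or dosing.

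Healthy controls, who are scanned but not dosed, are barred for "Any neurological disorder".

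**The concern.** Seizure is the main neurological hazard in the protocol's own risk text, and the entry rules address it through a diagnosis (seizure disorder), a time course (acute) and a degree (severe). A person can have a relevant history that meets none of the three. One seizure on study is enough to end participation, yet one seizure before the study does not bar entry. For such a patient, protection rests on the physician's discretion rather than on a rule.

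What is at stake is who may be dosed. Patients go home with a 7-day supply, and the top arm reaches 160 mg BID on day 4. Between visits they are followed by phone check-ins and video-observed dosing, so much of the protection has to come at entry. The protocol expects no direct benefit to participants, so excluding someone at avoidable risk takes no expected benefit from them.

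**Working it through.** The plan states no figure on this point. The main check is to hold hypothetical patients against every written rule.

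| Patient history | Exclusion 4 (acute) | Exclusion 5 (lifetime diagnosis) | Risk-minimization text (seizure disorder; severe condition) | Result |
|---|---|---|---|---|
| Acute neurological illness now | bars | – | – | excluded |
| Diagnosed seizure disorder, past or present | – | bars | bars | excluded |
| Severe neurological disease | – | – | bars | excluded |
| One past seizure, no seizure disorder diagnosed | no | no | no | admitted |
| Chronic, non-severe condition predisposing to seizure | no | no | no | admitted |

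Other rules narrow the last two rows without closing them. Exclusion 10 bars several drugs of the anticonvulsant type, so it catches only patients who take them. Exclusion 9 bars current substance abuse. A complete medical history is taken before MRI, but its stated purpose is to find renal disease, diabetes and hypertension.

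**The baseline scan.** Item b of the same procedure list says that a low eGFR or a positive pregnancy test ends participation. Item f states no such consequence for a gross structural brain abnormality. There is a console check on the day, but the neuroradiologist's screen may take up to 7 days. Drug is supplied once baseline procedures are complete, so dosing can start before that screen is back.

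**Scale of the hazard (context only).** Inputs are 6 seizures on POMA (Seizure Risk) and the exposure count: "Approximately 582 healthy subjects and 2877 subjects/patients with schizophrenia have been exposed to POMA in prior studies".
- Crude rate: 6/2877 = 0.21% (exact 95% CI 0.08% to 0.45%). Adding healthy subjects to the denominator gives 6/(2877 + 582) = 6/3459 = 0.17%.
- Chance of at least one seizure among N patients: 1 − (1 − p)^N. With p = 6/2877, N = 12 completers gives 2.5% (0.9% to 5.3%). N = 50, if everyone enrolled were dosed, gives 9.9% (3.8% to 20.3%).
- Seizures off POMA in the same programme: 1 + 1 + 3 = 5, with no denominator given.

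These rates ignore dose, length of exposure and background rate. They describe all patients, not the subgroup the rules miss. The documents give neither the size of that subgroup nor its seizure rate, so the effect of closing the gap cannot be computed.

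**The case against.** The strongest reply is that the plan already covers the most direct risk factor. Diagnosed seizure disorder is a lifetime exclusion, stated in the table and again in the risk text. Severe disease is excluded, study physicians screen every patient, and discontinuation criterion (c) allows removal on any clinical ground. All patients come through 6654R, under which eligibility screening is done, and it may already ask about past seizures or head injury. Nothing in the documents shows that a non-acute, non-severe neurological history raises seizure risk on POMA. All of this stands, and it makes the gap narrow. It does not supply a written rule for the two admitted rows above.

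Four stronger readings are tempting, and the documents do not support them.
- *Controls are better protected than the patients who take the drug.* The control rule mainly defines a healthy sample; that table also bars nearly all Axis I history and any past psychiatric medication. It does not plainly bar a single past seizure or a head injury either, so it is no benchmark for drug safety.
- *The top dose is twice the highest dose with a reported seizure, so risk is higher there.* Seizures were reported at 5, 20 and 80 mg BID, with no counts or denominators by dose. The protocol also reports no abnormal EEG activity up to 160 mg BID, and 44 patients who completed 160 to 480 mg BID for 7 days. That experience is too small to be reassuring: no seizure is listed at those doses, and 0 of 44 has a one-sided 95% upper bound of 1 − 0.05^(1/44) = 6.6%. It does rule out claiming a dose-response from these documents.
- *POMA causes seizures.* With 5 seizures off drug and no comparative rates, causation is unproven. The two convulsions that stopped the earlier study are presumably among the 6, since that count covers all human studies.
- *The 2.5% or 9.9% measures the gap.* Either figure would hardly change after the fix.

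**Conclusion.** The concern holds in a limited form. As written, the patient exclusions admit someone with a single undiagnosed past seizure, or with a chronic non-severe condition that predisposes to seizure. The protocol treats seizure as a recognised hazard and as a reason to stop.

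The size is unquantified: the number of such patients is unknown and, at ages 18 to 30 with 12 completers needed, probably small. The conclusion rests on reading the acute qualifier as applying to neurological disorder. It also assumes that 6654R, which is not available here, does not already impose a stricter rule. No effect on the CBV endpoint or the go/no-go decision is claimed.

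A reader might infer that patients should be barred for any neurological disorder at all. That goes too far, because it would exclude conditions such as migraine for which the documents show no link to seizure on this drug. This is a cheap improvement rather than a serious defect.

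**What to change.** Keep exclusion 4 as it is. In exclusion 5, keep hypertension and diabetes and replace the seizure part with: *any past seizure (other than simple childhood febrile seizure), or any current or past neurological condition judged by the study physician to raise seizure risk (for example a structural brain lesion or significant head injury)*. Give the method as medical history and physician exam.

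Add to Study Procedures, item f: *if the baseline scan shows a gross structural brain abnormality, POMA is not started, or is stopped if already started, unless the neuroradiologist and study physician document that it does not raise seizure risk.*

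If 6654R already applies an equivalent history screen, a cross-reference to it would do for the first change.

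The cost is one amendment: a reworded table row and an added sentence. History, examination and baseline MRI are already done, so no new test is needed. The downside is a few more screen failures.

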The Global Functioning Scale: Role (GFS: Role; Niendam, Beraden, Johnson & Cannon, 2006), and The Global Functioning Scale: Social (GFS: Social; Auther, Smith & Cornblatt, 2006) 5 min.

Clinical Global Impression scale (CGI)-3 minutes measures overall clinical functioning.

Columbia Suicide Severity Rating Scale (CSSRS)-5 minutes assesses for suicidality.

MATRICES-60-90 minutes is a comprehensive measure of cognitive functioning.

Wechsler Test of Adult Reading (WTAR)-5 minutes is a measure of intelligence.

Simpson Angus Scale (SAS) 5 min measures extrapyramidal symptoms

SAFTEE 5 min is a measure of side effects

Please attach copies, unless standard instruments are used

Off label and investigational use of drugs/devices

Choose from the following that will be applicable to your study

Drug

Select the number of drugs used in this study

1

Drug #1

Name of the drug

Pomaglumetad

Manufacturer and other information

Lilly and Denovo

Approval Status

IND is approved

IND#

134867

Who holds the IND/IND sponsor?

IND is held by PI/CU Investigator

[name]

Research Related Delay to Treatment

Will research procedures result in a delay to treatment?

No

Treatment to be provided at the end of the study

If subjects clinically require active treatment for new onset mood syndrome (major depressive or bipolar, anxiety symptoms, or psychosis during the study period or screening phase) patients will be immediately offered such treatment. Subjects will be ineligible for study participation if they meet any exclusion criteria as a result of such clinical developments. Since POMA is an experimental medication, it will not be available to subjects at the end of the trial.

Patients in this study will continue their usual treatment with their usual psychiatrist and clinician without interruption or changes. There is currently no standard best clinical practice (psychotherapeutic or psychopharmacologic) for prodromal stages of psychotic disease. Available antipsychotic therapies have been studied and are associated with improved prodromal symptoms and lessening of transition to psychosis, but are associated with a significant side-effect burden, including EPS, weight gain, and hyperlipidemia, amongst other side effects. The evidence for efficacy of cognitive-behavioral interventions for prevention of transition to psychosis is also mixed to date.

All COPE subjects receive up to 2 years of free, no cost treatment (medication management and therapy), though they would have to cover the cost of their medications.

Clinical Treatment Alternatives

Clinical treatment alternatives

If subjects clinically require active treatment for new onset mood syndrome (major depressive or bipolar, anxiety symptoms, or psychosis during the study period or screening phase) patients will be immediately offered such treatment. Subjects will be ineligible for study participation if they meet any exclusion criteria as a result of such clinical developments. Since POMA is an experimental medication, it will not be available to subjects at the end of the trial.

Patients in this study will continue their usual treatment with their usual psychiatrist and clinician without interruption or changes. There is currently no standard best clinical practice (psychotherapeutic or psychopharmacologic) for prodromal stages of psychotic disease. Available antipsychotic therapies have been studied and are associated with improved prodromal symptoms and lessening of transition to psychosis, but are associated with a significant side-effect burden, including EPS, weight gain, and hyperlipidemia, amongst other side effects. The evidence for efficacy of cognitive-behavioral interventions for prevention of transition to psychosis is also mixed to date.

Risks/Discomforts/Inconveniences

Risks that could be encountered during the study period

1) Risks and Discomforts Associated with LY2140023 (Pomaglumetd, "POMA") Administration

Approximately 582 healthy subjects and 2877 subjects/patients with schizophrenia have been exposed to POMA in prior studies. Across groups, nausea, vomiting, increased heart rate, and eosinophilia as assessed by laboratory values were commonly reported ($\geq 1\%$ and $< 10\%$) in patients treated with POMA.

Healthy controls: 582 healthy control subjects received doses ranging from an acute dose of 5mg to 200 bid for up to 14 days. Most of the adverse events reported were mild, and the subjects recovered without sequelae. The most common AEs ($\geq 10\%$) in clinical pharmacology studies conducted in healthy subjects were: nausea, headache, vomiting, and dizziness. The following SAEs have been reported in healthy subjects: infected sebaceous cyst (1), deep vein thrombosis (1), pulmonary embolism (2), and syncope due to vasovagal event (1). With the exception of syncope due to vasovagal event, none of these SAEs were reported by the investigator as related to administration of POMA.

Most pertinent to the proposed dose in this study, multiple doses of POMA, administered up to 160 mg BID, were well tolerated in the healthy subject population, including 5 healthy controls receiving 160 mg BID (greater or equal 320 mg per day) for 14 days and 2 receiving 200

mg bid without significant side effects. There were no serious adverse events and all subjects completed. The most commonly reported adverse events were headache, nausea, epistaxis, diarrhea, dizziness, somnolence, tremor, pruritus and feeling hot. The profile of drug-related adverse events were similar to those reported in previous clinical pharmacology studies in healthy volunteers, and those reported in clinical studies with patient populations. There were no dose limiting events observed in doses up to 160 mg BID. The study was terminated prematurely by the Sponsor in response to two cases of convulsions observed in an ongoing Phase 2 study in schizophrenia patients, involving dose levels lower than doses administered in this study. Although no serious adverse events occurred the healthy control dose escalation study, the decision was taken to stop the study whilst the 200 mg dose level was ongoing

There were generally no clinically significant values, changes, or trends in clinical laboratory data or vital signs. An increased eosinophil count was observed after 15 days of dosing with 40 mg POMA. However, similar eosinophil changes were not seen at higher dose levels, so there is no apparent dose dependency of the change. In addition, there were no concomitant cutaneous reactions associated with the eosinophil changes, so the clinical significance remains unclear. There were no clinically significant changes in ECGs which is consistent with findings, suggesting that doses of POMA up to 160 mg BID are not associated with QTc prolongation. This study incorporated EEG measurements to explore potential prodromal signs of convulsions at higher than previously administered doses of POMA. The results of the EEG measurements in this study showed that there was no abnormal EEG activity associated with POMA, administered up to 160 mg BID.

Patient populations: Table 6.4 from the IB (attached) provides a summary of TEAEs for patients who were assigned to take either placebo or POMA in completed studies. In the placebo-controlled studies, 727 patients were assigned to placebo, and 1555 were assigned to POMA. There was not a significant difference in adverse events when comparing patients taking placebo with patients taking POMA, 403 (55.4%) and 901 (57.9%), respectively. The common adverse events reported in $\geq 2\%$ of patients treated with POMA were: schizophrenia (underlying disease-related events), eosinophilia, anxiety, acute extrapyramidal symptoms, vomiting, abdominal pain, insomnia, headache, nausea, anxiety, blood CPK increased, agitation, constipation, abdominal pain, and dyspepsia. Nausea was significantly higher in the POMA pooled group compared with the placebo group (6.8% vs. 4.1%, $p=.005$), as were vomiting (4.1% vs. 2.5%, $p=.032$) and eosinophilia (4.8% vs. 1.0%, $p=.003$).

The most common TEAEs reported in $\geq 2\%$ of patients assigned to POMA in 1 or more of the completed long-term safety studies were: schizophrenia-related events, nausea, insomnia, headache, vomiting, nasopharyngitis, blood CPK increased, anxiety, decreased appetite, diarrhea, dizziness, tremor, fatigue, weight decreased, nasopharyngitis, upper respiratory tract infection, agitation, dyspepsia, bronchitis, back pain, cough, depression, restlessness, abdominal discomfort, blood pressure increased, constipation, rash, tooth ache, arthralgia, back pain, somnolence, akathisia, dry mouth, irritability, pruritus, and upper abdominal pain.

In the placebo-controlled studies there was a statistically higher incidence of abnormally high eosinophils at any time in the pooled POMA group compared with placebo (POMA 5.5%;

placebo 0.9%; $p < .001$). There was also a statistically significant mean increase in eosinophils during administration of POMA administration when compared to baseline or placebo.

The significance of the eosinophilia is unknown but there have been no clear clinical correlates to the eosinophil elevations. There have been no other consistent or clinically significant changes in laboratory values in the placebo-controlled studies.

In other studies, people who took compounds similar to POMA have experienced rash, skin itching, or skin peeling. Because of these experiences, rash, itching of the skin or skin peeling will be closely monitored. Subjects will be asked at every visit about these skin conditions.

Most pertinent to the present project, 44 patients with schizophrenia completed a multiple dose escalation study over a dose range of 160 to 480 mg BID for 7 days. The tolerability of POMA dosing was improved after the first day of dosing. In general, the TEAEs of nausea and vomiting occurred more frequently on first exposure to POMA. There was no apparent trend in the severity of TEAEs with increasing dose. The MTD for was not reached in this multiple ascending dose study. There were no clinically meaningful changes in ECG parameters and no positive correlation between plasma concentrations of POMA and changes from baseline in QTc across all the doses. A dose of 400 mg, which was approximately 5 times the anticipated clinical dose, did not prolong QTcF to a clinically significant degree.

Deaths: There were 18 deaths reported in completed studies (out of over 3000 human exposures). In these 18 death cases, 12 patients were assigned to take POMA, 3 patients were assigned to take placebo, 1 patient was assigned to take olanzapine, and 2 patients did not take any study drug. Also, of these 18 death cases, 7 were completed suicides with 5 of those patients assigned to take POMA. Of the 12 patients assigned to take POMA, 5 of those deaths occurred after the study drug had been held or discontinued. Also, of the 12 patients assigned to take POMA, 9 of those deaths were considered to be not related to the study drug treatment by the investigator, while all 12 deaths were considered to be not related to the study drug treatment by the sponsor. A listing of death cases for completed studies is presented in Table 6.1 in the IB (attached).

SAE: Overall, there were 361 case reports of SAEs (excluding the 18 deaths in patients) in POMA clinical trials. In the placebo-controlled studies, 727 patients were assigned to placebo, and 1555 were assigned to POMA. There was not a significant difference in SAEs when comparing patients taking placebo with patients assigned to POMA, 25 (3.4%) and 43 (2.8%), respectively. The only SAE reported $\geq 1\%$ patients was schizophrenia-related, with no statistically significant differences observed when comparing patients taking placebo with patients taking POMA.

Overdose: The effect of a single dose of activated charcoal on the PK of POMA and LY404039 was examined in healthy subjects. Activated charcoal reduced the area under the curve from time zero to infinity ($AUC_{0-\infty}$) and C_{max} of both POMA and LY404039 by approximately 25% and 35%, respectively, when administered 1 hour after a single 80-mg dose of POMA. However, the median time to maximum concentration (t_{max}) of neither analyte was affected by administration of activated charcoal.

Signs and Symptoms: There is limited information on signs or symptoms of POMA overdose or on treatment of overdose in humans. In clinical trials, 1 case of ingesting approximately 1800 mg of POMA in combination with lorazepam was reported. The patient did not experience any significant medical consequences of the overdose and spontaneously recovered without medical intervention.

Management of Overdose: No specific antidote is known. Symptomatic treatment and monitoring of vital organ function according to clinical presentation is recommended.

Risk of Serotonin Syndrome

POMA increases levels of serotonergic metabolites in humans (Lowe et al., 2012) and therefore there is a theoretical increased risk of serotonin syndrome when POMA is administered with a serotonergic medication, such as an antidepressant. There is insufficient experience in humans to know whether this risk of more than theoretical. However, in order to protect against this risk, we will review serotonin syndrome as part of the standard consent process with all patients, include a full paragraph in risks section of the consent form discussing this theoretical risk, and review side effects at every visit, as previously described. In addition, we are already excluding individuals with any severe medical condition or history of seizure disorder, and have implemented a robust schedule for adverse event monitoring, including safety labs and medical/physical examination.

Seizure Risk

In all of the studies performed with POMA in human subjects, events of seizure were reported in 6 patients treated with POMA at 5, 20, and 80 mg BID. Additionally, seizures were reported in 1 patient randomized to risperidone and 1 patient during a placebo-lead in period. Seizures were reported in an additional 3 patients prior to them being randomized to study medication. There was 1 additional report of convulsion that was determined not to be seizures.

Specific Vulnerabilities

There are no known specific vulnerabilities for a CHR (**clinical high risk**) population. However, we will obtain an independent assessment of capacity for all subjects, and will also perform the SIPS and CGI and GAF weekly while in the study to follow clinical status.

Risks and Discomforts Associated with Compound LY404039 in Humans

A breakdown product of POMA, called LY404039, has been given to 24 healthy people in a previous study. Experiences reported by 2 or more people who have taken LY404039 were headache, feeling dizzy upon standing up, stomach pain, nausea (feeling sick to the stomach), sore throat, tiredness, or feeling sleepy.

Risks and Discomforts Associated with LY2140023 (Pomaglumetad, "POMA") in Animals

POMA has been studied in animals. Rats treated with POMA showed uncoordinated movement, problems with walking, reduced body weight, uncontrollable and rapid shaking (convulsions or

